#### RESULTS

From May 2017 to May 2018, a total of 182 consecutive patients were screened for participation in this study, of whom 72 were excluded, while 110 patients constituted the study cohort and were randomized to one of two groups: stylet slow-pull technique (55 patients) and standard suction technique (55 patients) as showed in figure 1. Overall, there were 49 male (44.5%) and 61 female (55.5%), with a mean age of 70.9±11.3 years. Patients' and lesions' characteristics are shown in Table 1 and appeared similar in both groups. The majority of lesions were located in the head of the pancreas (72 lesions corresponding to 65.5%) with similar rates in slow-pull group (69%) and in the standard suction group (62%). No difference in mean size of the lesions was found between the two groups(35.9±19.9 vs 37.6±14.1 cm; p=ns).

Technical success was achieved in 95% of patients (slow pull technique 96% vs standard suction technique 94%, p=ns) with a not-significant blood contamination of the specimen in 85 patients (overall 77.3%: slow-pull 80% vs standard suction 74%, p=ns). A diagnosis of malignancy was obtained in 98 cases as showed in Table 2. Fifty were in the slow-pull group and 48 in the standard suction group. In 6 patients (1 in the slow-pull and 5 in the standard suction group) with a benign histological diagnosis at EUS-FNB the definitive diagnosis was chronic pancreatitis. Thus, these patients were considered true negative. Finally there were 6 false negative cases (4 in the slow pull technique group and 2 in standard suction group). Comparing the two groups (Table 3), the sensitivity, specificity, negative likelihood ratio, positive likelihood ratio, and diagnostic accuracy were 96 vs 93%, 100% vs 100%, 0.04 vs 0.07, "infinity" in both, and 96 vs 93%, respectively without any statistical difference between them. No procedure-related adverse events were observed in the two groups.

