#### **Outcome measures**

The primary end point of the study was the degree of blood contamination of the collected specimens in patients with pancreatic solid lesions who underwent EUS-FNB using the 20Gauge Procore Needle and the slow pulling or the standard aspiration techniques. Secondary outcomes were technical success, comparison of the performance of the two techniques during EUS-FNB in terms of sensitivity, specificity, positive predictive value (PPV), negative predictive value (NPV), and diagnostic accuracy, and occurrence of adverse events.

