#### **Outcome Definitions**

The degree of blood contamination of the specimen was based on the pathologist evaluation of the formalin fixed and paraffin embedded (FFPE) tissue samples and defined as significant when a large amount of blood cells made pathological diagnosis difficult to be made. On the other hand, blood contamination of the specimen was defined as not significant when no or only few blood cells were present without any influence on the pathological diagnosis.

Sensitivity was defined as the true positive rate whereby the test was the final cytologic diagnosis, Specificity as the true negative rate (proportion of actual negatives that are correctly identified as such), PPV was defined as the number of true positive divided the number of positive calls (true positive and false positive), NPV was defined as the number of true negative divided the number of negative calls (true negative and false negative). Diagnostic accuracy was defined as the ratio between the sum of true positive and true negative values divided by the total number of masses.

Technical success was defined as the capability of sampling the target lesion associated with the presence of a visible core, according to endosonographer's judgment, potentially useful for the final pathological analysis.

Adverse events were defined based on the criteria expressed by Cotton et al. [Cotton PB. Gastrointest Endosc 2010;71:446-54]

Samples positive for malignancy were considered diagnostic for malignancy, while in patients with negative EUS-FNB, surgical specimen evaluation, results of other diagnostic investigations and/or a clinical follow-up of at least 6 months were used to establish the definitive diagnosis.

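### RESULTS: the printed sensitivity, accuracy and negative likelihood ratio are the mirror image, by arm, of what the section's own labelled patient counts give

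*Combined protocol and SAP*

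**What the plan says.** The Outcome measures section names diagnostic performance as a secondary outcome: "sensitivity, specificity, positive predictive value (PPV), negative predictive value (NPV), and diagnostic accuracy". The Outcome Definitions section defines each measure; for example, "NPV was defined as the number of true negative divided the number of negative calls (true negative and false negative".

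The RESULTS section gives the randomised groups as "stylet slow-pull technique (55 patients) and standard suction technique (55 patients". It then labels three sets of counts by arm:

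- Malignant diagnoses: "Fifty were in the slow-pull group and 48 in the standard suction group".
- Benign results confirmed as chronic pancreatitis and treated as true negatives: "1 in the slow-pull and 5 in the standard suction group".
- False negatives: "6 false negative cases (4 in the slow pull technique group and 2 in standard suction group".

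The next sentence refers to Table 3 and gives the performance figures, starting with sensitivity and specificity: "negative likelihood ratio, positive likelihood ratio, and diagnostic accuracy were 96 vs 93%, 100% vs 100%, 0.04 vs 0.07". The accuracy pair that follows is again 96 vs 93%. That sentence does not name the arms. Comparisons in the same section that do name them put slow-pull first, for example technical success: "slow pull technique 96% vs standard suction technique 94%, p=ns".

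**The concern.** A reader will take the performance figures in the order used in the sentences just before them, slow-pull then suction. Read that way, slow-pull has the higher sensitivity and accuracy. Yet slow-pull is also the arm said to have four false negatives against two, with nearly the same number of malignant lesions. Both cannot be right.

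The direction of a named secondary outcome is at stake, and so is the use of the data by others. Someone building per-arm 2×2 tables for a pooled analysis would get opposite tables from the counts and from the percentages, and pooling uses the sign of an estimate whether or not it is significant. If the counts rather than the percentages were misassigned, arm labels would be wrong on the diagnostic classification of all 110 patients. That should be ruled out against source records.

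**Working it through.** **Inputs (RESULTS, as labelled)**

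| | Slow-pull | Suction |
|---|---|---|
| True positive (TP) | 50 | 48 |
| True negative (TN) | 1 | 5 |
| False negative (FN) | 4 | 2 |
| Total | 55 | 55 |

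The totals equal the randomised numbers, so the counts are complete. False positives are zero: the Outcome Definitions section accepts a malignant sample as diagnostic, and specificity is printed as 100% in both arms.

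**Formulas.** Sensitivity = TP/(TP+FN). Accuracy = (TP+TN)/N. Negative likelihood ratio (LR−) = (1 − sensitivity)/specificity, which is FN/(TP+FN) when specificity is 1. NPV = TN/(TN+FN).

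**Results against the printed pairs**

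| | Slow-pull, from counts | Suction, from counts | Printed pair |
|---|---|---|---|
| Sensitivity | 50/54 = 92.6% | 48/50 = 96.0% | 96 vs 93% |
| Accuracy | 51/55 = 92.7% | 53/55 = 96.4% | 96 vs 93% |
| LR− | 4/54 = 0.074 | 2/50 = 0.040 | 0.04 vs 0.07 |

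In slow-pull-first order none of the three pairs reproduces. Reversed, all three match to the printed rounding. This is one transposition rather than three errors: with no false positives, all three measures turn on the 4 vs 2 false negatives.

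**Could a smaller slip in the counts explain it?** Arms below are slow-pull, then suction, after the exchange.

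- FN exchanged alone: totals 53 and 57; sensitivity 50/52 = 96.2% and 48/52 = 92.3%; LR− 0.038 and 0.077. These fit neither the printed 93% and 0.07 nor 55 per arm.
- TN and FN exchanged: totals 57 and 53, with the same sensitivities and LR−.
- TP and FN exchanged: sensitivity 48/50 = 96.0% and 50/54 = 92.6% would fit, but the totals become 48+1+2 = 51 and 50+5+4 = 59.
- False negatives assumed to lie within the 98 malignancies: sensitivity 46/50 = 92.0% and 46/48 = 95.8%, still in the opposite order, with totals of 51 and 53 that leave six patients unaccounted for.
- TP, TN and FN all exchanged: totals 55 and 55; sensitivity 96.0% and 92.6%; accuracy 96.4% and 92.7%; LR− 0.040 and 0.074. This matches the printed order.

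So either all three sets of counts are on the wrong arms, or the counts are right and the printed pairs run suction first.

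**Size, slow-pull minus suction, on the labelled counts** (Newcombe 95% CI, Fisher's exact p)

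- Sensitivity: −3.4 points (−14.0 to +7.1), p = 0.68.
- Accuracy: −3.6 points (−14.0 to +6.1), p = 0.68.
- The printed figures read slow-pull first imply 96 − 93 = +3 points for each.

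**NPV.** It is a named secondary outcome that the results text does not print, so readers must derive it. As labelled it is 1/5 = 20.0% for slow-pull and 5/7 = 71.4% for suction, a difference of −51.4 points (−77.6 to +3.9, p = 0.24). If the counts are exchanged, so are these values.

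**Primary endpoint.** The labelled percentages without significant blood contamination correspond to 44/55 and 41/55, and 44 + 41 = 85, the printed total. Nothing there conflicts.

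**The case against.** The sentence names no arm. Read suction first, every printed value is correct, so no number is demonstrably wrong. The section has another unlabelled pair (mean lesion size), so the text does not formally fix the order of unlabelled pairs. Table 3, which the sentence cites, is missing from the text reviewed and may label the arms properly. A wrong set of counts would need three separately labelled statements all to be exchanged; one reversed sentence is the simpler explanation. The difference is two false negatives on a secondary outcome, with p about 0.68 under either assignment. The NPV gap rests on 5 and 7 negative calls and partly reflects how many chronic pancreatitis patients fell in each arm.

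Most of this stands as a limit on the claim. A single reversed sentence is the simplest reading, and Table 3 may settle the matter. The NPV figure shows how much depends on the arm labels; it is not a contradiction in the printed text and does not measure the size of the error. None of this removes the defect. An unlabelled sentence that runs against the order of every labelled comparison around it credits each technique with the other's results, and the reader has no cue to the change.

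**Conclusion.** The concern holds. In the order the RESULTS section uses whenever it names the arms, its sensitivity, accuracy and negative likelihood ratio contradict its own labelled counts. The contradiction reverses the sign of the difference: −3.4 points (sensitivity) and −3.6 points (accuracy) for slow-pull by the counts, against about +3 for each by the printed pairs.

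This rests on two assumptions: that the unlabelled sentence follows the slow-pull-first order, and that there were no false positives, as the printed 100% specificity implies. The mismatch is certain under those assumptions; which set is misassigned cannot be determined from the documents. The conclusion of no statistical difference is unaffected, as is the primary endpoint. It should be fixed because it reverses the apparent direction of named secondary outcomes.

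**What to change.** Check the per-arm TP, TN and FN counts and Table 3 against the randomisation list and the study database. Correct whichever set proves to be misassigned; if the counts are wrong, all three must be exchanged together to keep 55 per arm. If only the order of the sentence is at fault, reorder it. Recompute sensitivity, accuracy, negative likelihood ratio and NPV from the verified counts. In every case, name the arms beside each figure, in the form: slow-pull x% vs standard suction y%.

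The cost is a check of existing records and one corrected sentence, plus Table 3 if it is affected. No new data are required.

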# **Statistical Analysis**

The sample size was calculated based on the results of a previous study [Nakai Y. Dig Dis Sci. 2014;59:1578-85] that showed that blood contamination of the specimen was lower with the stylet slow-pull technique as compared with the standard suction technique (25% vs 70%), with a consequent increase in the diagnostic accuracy. Based on these data we calculated for a difference of 25%, at a power of 80% and an alpha of 0.05 (two-sided test), a final sample size of 110 patients (55 patients in each group). Continuous variables will be reported as mean ± standard deviation (SD). Categorical variables will be presented as numbers and percentage and will be compared either using the chi-square test (with Yates' correction when appropriate) or Fisher exact test.

Statistical was conducted using the Fisher's exact test for categorical variables and the Mann–Whitney U-test for continuous variables. Sensitivity, specificity, positive predictive value (PPV), negative predictive value (NPV), and overall diagnostic accuracy for each arm were investigated by comparing the results with the definitive diagnosis. Statistical tests were considered

significant at a corresponding p value of <0.05. Data handling and analyses were done with SPSS 14.

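### PPV and NPV are planned secondary outcomes, but the results text gives unplanned likelihood ratios instead; the printed counts give a pooled NPV of 6/12 (50%), and their arm labels conflict with the printed percentages.

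*Combined protocol and SAP*

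**What the plan says.** Three sections of the combined protocol and SAP commit to the predictive values. Outcome measures lists "sensitivity, specificity, positive predictive value (PPV), negative predictive value (NPV), and diagnostic accuracy, and occurrence of adverse events" among the secondary outcomes. Outcome Definitions defines both; for the negative one, "NPV was defined as the number of true negative divided the number of negative calls (true negative and false negative"). Statistical Analysis says that "negative predictive value (NPV), and overall diagnostic accuracy for each arm were investigated by comparing the results with the definitive diagnosis". None of the three mentions a likelihood ratio.

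The Results section points to Table 3 and then states that "the sensitivity, specificity, negative likelihood ratio, positive likelihood ratio, and diagnostic accuracy were 96 vs 93" per cent. It gives negative likelihood ratios of 0.04 vs 0.07, infinite positive likelihood ratios and specificity of 100% in both arms, and reports no statistical difference. Neither PPV nor NPV appears in that text. The section does print true positives, true negatives and false negatives by arm.

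**The concern.** A planned and defined secondary outcome should appear where the diagnostic results are summarised, and a measure outside the plan should be marked as such. Here the text does neither.

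The choice matters because a likelihood ratio and an NPV answer different questions when nearly everyone has the disease. A negative likelihood ratio of 0.04 or 0.07, read without the prevalence, can suggest that a negative result is close to conclusive. NPV shows directly how often the negative results were right, and on these counts that was half the time.

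There is a second problem in the same sentence. The percentages and the counts run in opposite arm order, so an NPV for either arm cannot be trusted until that is settled.

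**Working it through.** **Inputs (Results section).** Slow-pull: 50 true positives (TP), 1 true negative (TN), 4 false negatives (FN). Suction: 48 TP, 5 TN, 2 FN. There are no false positives (FP), as the printed specificity of 100% implies. The counts close: 50 + 1 + 4 = 55 and 48 + 5 + 2 = 55, the numbers randomised.

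**Reproducing the printed figures.** Sensitivity = TP/(TP + FN). Accuracy = (TP + TN)/N, as in Outcome Definitions. Negative likelihood ratio (LR−) = (1 − sensitivity)/specificity.

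| Measure | Slow-pull, from counts | Suction, from counts | Printed order (slow-pull vs suction) |
|---|---|---|---|
| Sensitivity | 50/54 = 92.6% | 48/50 = 96.0% | 96 vs 93% |
| LR− | (4/54)/1 = 0.074 | (2/50)/1 = 0.040 | 0.04 vs 0.07 |
| Accuracy | 51/55 = 92.7% | 53/55 = 96.4% | 96 vs 93% |

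All three match only with the arms exchanged. Exchanging the false negatives alone does not repair this: the arms would total 50 + 1 + 2 = 53 and 48 + 5 + 4 = 57. So either the whole set of counts or the set of percentages is attached to the wrong arms.

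**The planned measures.** PPV = TP/(TP + FP) and NPV = TN/(TN + FN), with exact (Clopper-Pearson) 95% intervals.

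- PPV: 50/50 and 48/48, 100% in both arms.
- NPV, slow-pull as labelled: 1/(1 + 4) = 20.0% (0.5% to 71.6%).
- NPV, suction as labelled: 5/(5 + 2) = 71.4% (29.0% to 96.3%).
- NPV, pooled: 6/12 = 50% (21% to 79%).

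If the count labels are the error, the two arm values change places. The pooled value stays the same.

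**Comparison of arms.** Statistical Analysis names Fisher's exact test: "Statistical was conducted using the Fisher's exact test for categorical variables". On 1 of 5 against 5 of 7 it gives a two-sided p = 0.24. For sensitivity and accuracy it gives p = 0.68 each. None is "significant at a corresponding p value of <0.05".

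**Why LR− and NPV read so differently.** Malignancy prevalence is (98 + 6)/110 = 104/110 = 94.5%, so the pre-test odds are 104/6 = 17.3. The pooled LR− is (6/104)/1 = 0.058. The post-test odds are 17.3 × 0.058 = 1.0, a 50% probability of malignancy after a negative result. The low ratio and the 50% NPV are the same data.

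**Case mix.** As labelled, prevalence is 54/55 = 98.2% for slow-pull and 50/55 = 90.9% for suction, that is, 1 against 5 benign cases. NPV depends on prevalence, so part of the gap between arms comes from this imbalance.

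**Inadequate samples.** Technical success of 96% and 94% of 55 corresponds to 53 and 52 patients, leaving about 5 of 110 without an adequate visible core. Yet 98 + 6 + 6 = 110, so everyone is in the diagnostic counts. The documents do not say where these patients fall. If none of them is among the false negatives, 6/12 = 50% describes adequate samples. If all 5 are, NPV among adequate samples would be 6/(6 + 1) = 86%. That range is an assumption, not a finding.

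**The case against.** The strongest reply is that Table 3 may give PPV and NPV. That stands: only the text of the Results section can be judged, and if the table has them, the remaining work is to bring them into the text with denominators and intervals. It is also true that the counts are printed, so any reader can derive NPV, although a planned outcome should not be left to the reader to compute.

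Three stronger readings are tempting, and the documents support none of them.

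- A reader might infer selective reporting, with a less flattering measure exchanged for a better-looking one. The documents show an unexplained substitution and say nothing of motive. PPV, equally planned and equally absent from the text, is 100% in both arms, and the true and false negatives are printed openly.
- A reader might take 20% against 71% as contradicting the statement of no statistical difference, or as a technique effect. It is neither: p = 0.24 on 12 results, overlapping intervals, unequal case mix and unsettled labels.
- A reader might say that NPV reverses the trial's practical message on negative biopsies. The Results section states no such message, so there is nothing to reverse.

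A further caution stands. Only the six true negatives are described as benign on histology. What the six false negatives showed is not stated, and some may be inadequate samples. They are better called non-positive results than benign readings.

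**Conclusion.** The point holds as a reporting fault in secondary outcomes, together with an arm-label conflict that must be resolved first. PPV and NPV are planned and absent from the Results text; the likelihood ratios are present and unplanned. The secure figure is the pooled NPV of 6/12 = 50% (21% to 79%) at 94.5% prevalence, which does not depend on the arm labels. The arm values, 1/5 and 5/7, hold only if the printed count labels are right, and even then they do not separate the techniques.

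The conclusion rests on the counts being correct apart from their labels, on there being no false positives, and on the classification of all 110 patients as printed. It does not affect the primary endpoint, and it covers the Results text only, since Table 3 was not available.

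**What to change.** In this order:

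1. Check the source data, establish whether the counts or the percentages carry the wrong arm labels, and correct the text and Table 3 accordingly. Until then, report no NPV by arm.
2. Report PPV and NPV per arm and pooled, with numerators, denominators and exact 95% intervals, in the text and, if absent, in Table 3.
3. Give the number of benign cases per arm and the malignancy prevalence beside them, and say that NPV depends on that prevalence.
4. Label the likelihood ratios as post hoc.
5. State that 6 of 12 non-positive results were false negatives, and how patients without an adequate sample were classified.

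The tabulation takes a few lines from existing counts. The label check and the classification of inadequate samples require a return to the patient records. The downside is a less favourable figure for negative biopsies than the likelihood ratios suggest.
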